11.8.2 Deaths and Serious Adverse Events

Treatment-emergent SAEs, IP-related treatment-emergent SAEs, serious hypoglycemic TEAEs (Table 6, Analysis 10), and IP-related Serious hypoglycemic TEAEs will be summarized separately by preferred term for the SS (Table 6, Analysis 11). All SAEs recorded on the CRF will be listed for subjects in the SS.

A table presenting the number and percentage of subjects by preferred term who experienced fatal TEAEs during the study will be presented for the SS. A further summary of Serious treatment-emergent SAEs by preferred term will be provided. Deaths occurring in the study will also be listed for all subjects in the SS.

Sponsor: Gan & Lee Pharmaceuticals, USA Corporation
 Protocol no: GL-GLAT2-3002

Statistical Analysis Plan
 Version Date: 16-Nov-2020

11.8.3 Laboratory Data

Laboratory test results will be reported in International System of Units (SI) units. For observed values below the lower limit of quantification/detection (for example total bilirubin reported as $<3 \mu\text{mol/L}$), the lower limit ($3 \mu\text{mol/L}$) will be used as the imputed value.

Laboratory values and change from baseline will be summarized using descriptive statistics by time point and treatment group. Hematology, chemistry, thyroid stimulating hormone (TSH) and free thyroxine (T4) results will be collected during screening, at visit Week 12 and visit Week 26.

Shift tables of the maximum post-baseline value will be presented by treatment group, reference range and time point. Shift tables will include all laboratory assessments. In addition, subject listings of abnormal (grade ≥ 3) post-baseline laboratory toxicities will be provided. Standard ranges from the central laboratory will be used for the laboratory analysis.

Lab assessments will be grouped for summary as follows:

- Hematology – white blood cell (WBC) parameters: WBC count and differentials
- Hematology – red blood cell (RBC) parameters: hemoglobin, hematocrit, RBC count, mean corpuscular hemoglobin, mean corpuscular hemoglobin concentration, mean corpuscular volume
- Hematology – other parameters: platelets
- Serum chemistry – hepatobiliary parameters: alanine aminotransferase (ALT), aspartate aminotransferase (AST), total bilirubin, alkaline phosphatase
- Serum chemistry – general chemistry: sodium, potassium, chloride, bicarbonate, total protein, calcium, creatine kinase, total cholesterol, high-density lipoprotein, low-density lipoprotein, triglycerides
- Serum chemistry – renal function tests: urea, creatinine
- Thyroid – free T4, TSH

A summary assessing the potential hepatotoxicity and potential Hy's Law will be presented. A listing of these potentially hepatotoxic values (along with the corresponding amount times upper limit normal) will be presented.

A treatment-related laboratory result listing including weight, HbA1c, fasting blood glucose, and immunogenicity results will be provided. Assessments after EOT visit will be flagged in the listing.

Positive pregnancy results and dip-stick urinalysis results will be provided in a listing.

11.8.3.1 NCI CTCAE Grading

Where laboratory values are categorized into NCI CTCAE v4.03 grades, the categories are defined according to the criteria available on the following website:

<http://evs.nci.nih.gov/ftp1/CTCAE/About.html>

Note that grades are applied based only on the numeric SI value of the parameter assessed; clinical signs and symptoms are not considered. For example, Grade 4 hyperglycemia will be assigned based solely on the value of the glucose measurement, and acidosis will not be considered. Where categories are distinguished only by clinical signs or symptoms, the lowest of the possible grades will be assigned.

NCI CTCAE grades will be applied for the following lab parameters (as defined by the table in Appendix 2):

Hematology: hemoglobin (anemia), total WBC (leukopenia and leukocytosis), lymphocytes (lymphopenia), neutrophils (neutropenia), and platelets (thrombocytopenia).

Percent lymphocytes and percent neutrophils were specified in the original protocol and consequently absolute lymphocyte and neutrophil counts with corresponding normal ranges needed for the derivation of NCI CTCAE grading were not included in the central laboratory data transfers. Absolute counts for lymphocytes and neutrophils will be derived based on percent values and total WBC count as defined below only for the purpose of NCI CTCAE grading (Blumenreich, M. 1990 (9)). Calculated values will be rounded to the thousandths. NCI CTCAE grading will be derived in three steps: 1) grades 2-4 will be derived according to NCI CTCAE cutoffs, 2) if the reference range indicator for percent value indicates "LOW" and the derived absolute count is greater than 0.8 ($10^9/L$) for lymphocytes or 1.5 ($10^9/L$) for neutrophils then grade=1, and then 3) if the reference range indicator for percent value is 'NORMAL' then grade=0.

$$\text{Absolute lymphocyte count } (10^9/L) = (\text{total WBC } (10^9/L) * \% \text{ Lymphocyte})/100$$

$$\text{Absolute neutrophil count } (10^9/L) = (\text{total WBC } (10^9/L) * \% \text{ Neutrophil})/100$$

Chemistry: alkaline phosphatase, ALT, AST, bilirubin, calcium (hypocalcemia, hypercalcemia), creatinine, glucose (hyperglycemia, hypoglycemia), potassium (hyperkalemia, hypokalemia), sodium (hyponatremia, hypernatremia), and triglycerides (hypertriglyceridemia).

Laboratory measurements that are within the limits of normal and are not graded as 1-4, per the NCI CTCAE, will be coded as "Grade 0," which is defined as normal.

11.8.4 Vital Signs

Values and change from baseline in vital signs will be summarized by time point and treatment group. Descriptive statistics will be shown for baseline, visit Week 2, visit Week 4, visit Week 8, visit Week 12, visit Week 16, visit Week 20 and visit Week 26. Parameters include systolic and diastolic blood pressure, and pulse.

Potentially clinically significant vital signs results will be summarized and will include the following categories:

- Pulse < 50 beats per minute
- Pulse > 120 beats per minute
- Pulse \geq 30 beats per minute increase from baseline
- Pulse \geq 30 beats per minute decrease from baseline
- Systolic blood pressure > 150 mmHg or diastolic blood pressure > 100 mmHg
- Systolic blood pressure > 200 mmHg or diastolic blood pressure > 110 mmHg
- Weight \geq 5% increase from baseline
- Weight \geq 5% decrease from baseline

A listing of the observations with potentially clinically significant vital sign results will be provided.

Sponsor: Gan & Lee Pharmaceuticals, USA Corporation
 Protocol no: GL-GLAT2-3002

Statistical Analysis Plan
 Version Date: 16-Nov-2020

11.8.5 Electrocardiograms

Values and change from baseline in ECG results will be summarized by time point and the treatment group. Descriptive statistics will be shown for baseline and visit Week 26. Potentially clinically significant ECG results will be summarized and will include the following categories:

- Heart rate < 50 beats per minute
- Heart rate > 100 beats per minute
- PR Interval \geq 200 msec
- QRS Interval \geq 200 msec
- QT Interval \geq 200 msec
- QT Interval change from baseline \geq 30 msec - < 60 msec
- QT Interval change from baseline \geq 60 msec
- Corrected QT using Fridericia's formula (QTcF) Interval \geq 450 - < 480 msec
- QTcF Interval \geq 480 - < 500 msec
- QTcF Interval \geq 500 msec
- Corrected QT using Bazett's formula (QTcB) Interval \geq 450 - < 480 msec
- QTcB Interval \geq 480 - < 500 msec
- QTcB Interval \geq 500 msec

where $QTcF = QT / [(heart\ rate/60)^{(1/3)}]$ and $QTcB = QT / [(heart\ rate/60)^{(1/2)}]$.

A listing of the observations with potentially clinically significant ECG results will be provided.

12. Validation

PRA's goal is to ensure that each TFL delivery is submitted to the highest level of quality. Our quality control procedures will be documented separately in the study specific quality control plan.

13. References

1. Chow, S-C, Shao, J. A note on statistical methods for assessing therapeutic equivalence. *Controlled Clinical Trials*. 2002; 23(5):515-520.
2. East 6 (2020). Statistical software for the design, simulation and monitoring clinical trials. Cytel Inc., Cambridge MA.
3. American Diabetes Association Issues Hypoglycemia Position Statement. American Diabetes Association Website. <https://care.diabetesjournals.org/content/diacare/early/2016/11/09/dc16-2215.full.pdf>. Diabetes Care. ePublished November 21, 2016.

Gan & Lee Pharmaceuticals USA

PRA HEALTH SCIENCES

Sponsor: Gan & Lee Pharmaceuticals, USA Corporation
Protocol no: GL-GLAT2-3002

Statistical Analysis Plan
Version Date: 16-Nov-2020

5. Matts, JP and Lachin, J M. 'Properties of permuted-block randomization in clinical trials', *Controlled Clinical Trials*. 1988, 9(4): 327–344.

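### SAP 11.8.5 writes both QT heart-rate corrections upside down, and its raw QT cut-off of 200 msec is too low to separate any ECG from the rest

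*SAP*

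**What the plan says.** SAP 11.8.5 introduces its flagging list with "Potentially clinically significant ECG results will be summarized and will include the following categories". The list has:

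- heart rate below 50 and above 100;
- "PR Interval \geq 200 msec", QRS at the same figure, and then "QT Interval \geq 200 msec";
- two bands for change in QT from baseline;
- three bands each for QTcF and QTcB, starting with "Corrected QT using Fridericia's formula (QTcF) Interval \geq 450 - < 480 msec" and "Corrected QT using Bazett's formula (QTcB) Interval \geq 450 - < 480 msec" and rising through 480 to 500 msec.

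Below the list the two corrections are defined. The Fridericia one begins "QTcF = QT / [(heart\ rate/60)^{(1/3" and the Bazett one "QTcB = QT / [(heart\ rate/60)^{(1/2" (closing brackets omitted here). Both put heart rate over 60 in the denominator. The section ends: "A listing of the observations with potentially clinically significant ECG results will be provided".

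Appendix 2 of the SAP also starts QTc grading at 450 ms. Protocol 10.4 says that heart rate, QT and a corrected QT are recorded from each ECG. Neither document states the corrections in RR form or amends them elsewhere.

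**The concern.** A heart-rate correction estimates what QT would be at 60 bpm. QT shortens as the heart speeds up, so the correction has to raise QT above 60 bpm and lower it below 60 bpm. The printed formulas do the opposite. They shorten an already short QT at fast rates and lengthen an already long one at slow rates. The QTc rows can then miss prolongation in subjects with faster hearts and show false prolongation in subjects with slower hearts.

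The raw QT row is a separate defect. A threshold that nearly every ECG exceeds tells the reader nothing about a subject or an arm, and it fills the listing with unremarkable tracings.

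The incidence of clinically significant ECG abnormalities is a secondary safety endpoint (Protocol 8.7.3.2, SAP 6.3.2). These categories are the only numerical thresholds that the SAP's ECG section sets for summarising such results.

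**Working it through.** **Inputs.** The formulas, the QTc bands (450, 480, 500 msec), the raw QT cut-off (200 msec) and the heart-rate limits (50 and 100 bpm) all come from SAP 11.8.5. The QT values of 400 and 430 msec are illustrations.

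**Formulas.** Let p = 1/3 for QTcF and 1/2 for QTcB.

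- SAP form: QT / (HR/60)^p
- RR form: QT / (60/HR)^p = QT × (HR/60)^p
- Ratio of RR form to SAP form: (HR/60)^(2p), which is (HR/60)^(2/3) for QTcF and HR/60 for QTcB

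The ratio is 1 only at 60 bpm. At 75 bpm it is 1.160 (QTcF) and 1.250 (QTcB). At 100 bpm it is 1.406 and 1.667. At 50 bpm it is 0.886 and 0.833.

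**One case in full: QT 400, 100 bpm.** HR/60 = 1.6667, with cube root 1.1856 and square root 1.2910.

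- SAP form: 400/1.1856 = 337 and 400/1.2910 = 310
- RR form: 400 × 1.1856 = 474 and 400 × 1.2910 = 516

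**Other cases (msec).**

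| QT | HR | SAP QTcF / QTcB | RR QTcF / QTcB | Effect on bands |
|---|---|---|---|---|
| 400 | 75 | 371 / 358 | 431 / 447 | none; all below 450 |
| 400 | 90 | 349 / 327 | 458 / 490 | 450-<480 and 480-<500 missed |
| 400 | 100 | 337 / 310 | 474 / 516 | 450-<480 and ≥500 missed |
| 430 | 50 | 457 / 471 | 405 / 393 | falsely placed in both 450-<480 rows |

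**Raw QT needed to enter the 450 band (QTcF / QTcB).**

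- At 90 bpm: 515 / 551 under the SAP form, 393 / 367 under the RR form
- At 50 bpm: 423 / 411 under the SAP form, 478 / 493 under the RR form

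**The raw QT row.** At 60 bpm QT equals QTc under either form, so the cut-off lies 450 − 200 = 250 msec below the lowest QTc band. Over 50-100 bpm, in RR form, a QT of 200 corrects to:

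- Fridericia: 188 to 237
- Bazett: 183 to 258

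To reach 450, a QT of 200 would need a heart rate of 60 × (450/200)^3 = 683 bpm by Fridericia, or 60 × (450/200)^2 = 304 bpm by Bazett.

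**Share flagged.** The documents give no QT distribution. Assume it is roughly normal with mean 350-400 and SD 30-40 msec. The least extreme corner, mean 350 and SD 40, gives z = (200 − 350)/40 = −3.75, so 99.991% lie above the cut-off. The other settings checked give more.

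**The case against.** Several points against the concern are sound.

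- **Reach within the table.** The heart-rate, PR, QRS and QT change-from-baseline rows use neither the formulas nor the raw QT cut-off. A reader might infer that the whole ECG table fails. It does not.
- **Moderate rates.** At 75 bpm with QT 400 the corrected values differ by 60 msec (QTcF) and 89 msec (QTcB), but no band changes. Misclassification depends on how far heart rate is from 60 and how close QTc is to a band limit.
- **Participant safety.** A reader might infer that the error affected care. The documents do not support this. SAP 10.3 dates the last follow-up to 13 August 2019, before this November 2020 SAP. Under Protocol 10.4 and 11.5.2, ECG findings were judged by the investigator and reported as adverse events.
- **Comparison of arms.** Both arms use the same formula, so bias between them is not shown.
- **Recorded QTc.** Protocol 10.4 collects a corrected QT. If programmers tabulate that value, the printed formulas may never reach the tables.

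The last point limits the consequence but does not remove the error. The SAP defines QTcF and QTcB by these formulas and does not say that a recorded value takes precedence, and the raw QT row is wrong either way. A text-extraction fault is unlikely because both formulas have the same orientation, although the source page should be checked.

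**Conclusion.** Wrong as written; should be fixed. Both corrections are the reciprocal of the methods they name. This is algebra and rests on no data. It affects the six QTcF and QTcB rows and any QTc summary or change from baseline derived the same way. In the worked cases the error is 137 msec (QTcF) and 206 msec (QTcB) too low at 100 bpm, and 52 and 78 msec too high at 50 bpm, taken from the rounded values above.

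That the raw QT row cannot discriminate follows from its distance to the SAP's own bands. The figure of over 99.99% flagged rests on the assumed QT distribution. The repeated 200 in the PR, QRS and QT rows may mean that a figure was copied down, but the documents do not show this.

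A reader might treat this as a threat to the trial's conclusions. It is not one: the output is descriptive, and neither the primary immunogenicity analysis nor the key secondary HbA1c analysis uses it. How many subjects would change category cannot be known without the ECG data.

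**What to change.** In SAP 11.8.5:

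1. Write QTcF = QT/(60/HR)^(1/3) and QTcB = QT/(60/HR)^(1/2).
2. Recompute both from the recorded QT and heart rate, and state that these derived values feed the tables and listing.
3. Have the sponsor remove the raw QT row at 200 msec, or reconcile it with the 450/480/500 bands in the same list and give the reason. No replacement threshold is proposed here.

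The cost is two formulas and one row in the SAP, with matching changes to the table shells and programs. No new data are needed, because heart rate and QT are already collected. SAP sections 3 and 10.3 place this version before database lock, so the change can be made before the final tables are run.

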Metabolism and nutrition disorders	Hypertriglyceridemia	Serum triglycerids 150 mg/dL - 300 mg/dL; 1.71 mmol/L - 3.42 mmol/L	Serum triglycerids >300 mg/dL - 500 mg/dL; >3.42 mmol/L - 5.7 mmol/L	Serum triglycerids >500 mg/dL - 1000 mg/dL; >5.7 mmol/L - 11.4 mmol/L	Serum triglycerids > 1000 mg/dL; >11.4 mmol/L; life-threatening consequences
Investigations	Electrocardiogram QT corrected interval prolonged	QTc 450-480 ms	QTc 481-500 ms	QTc ≥ 501 ms on at least 2 separate ECGs	QTc ≥ 501 ms or >60 ms change from baseline and Torsade de pointes or polymorphic ventricular tachycardia or signs/symptoms of serious arrhythmia

AE = adverse event; CTCAE = Common Terminology Criteria for Adverse Events; ECG = electrocardiogram; Hgb = hemoglobin; LLN = lower limit of normal; QTc = corrected QT interval; SOC = system organ class; ULN = upper limit of normal;

Note: Laboratory measurements that are within the institutional limits of normal and are not graded as 1-4, per the CTCAE, will be summarized as "Grade 0" which is defined as normal.

Sponsor: Gan & Lee Pharmaceuticals, USA Corporation
Protocol no: GL-GLAT2-3002

Statistical Analysis Plan
Version Date: 16-Nov-2020

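### The two ECG change-from-baseline categories are on uncorrected QT, so heart rate alone can create or hide a flag; moving them to QTc works only if the printed QTc formulas are corrected too.

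*SAP*

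**What the plan says.** SAP 11.8.5 lists categories for potentially clinically significant ECG results. Two of them compare a subject with his or her own baseline, and both are worded as "QT Interval change from baseline": "QT Interval change from baseline \geq 30 msec - < 60 msec" and "QT Interval change from baseline \geq 60 msec". The same list names the corrected intervals separately, as "Corrected QT using Fridericia's formula (QTcF) Interval" and "Corrected QT using Bazett's formula (QTcB) Interval", so QT Interval without a qualifier means the uncorrected interval. Each corrected interval has three absolute bands (450 to under 480, 480 to under 500, and 500 msec or more). Neither has a change category, and none appears elsewhere in the SAP's planned ECG analyses.

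The section opens with a general statement that ECG values and changes from baseline will be summarized descriptively, for baseline and Week 26. It sets no threshold and does not name QTc.

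The section also prints the two correction formulas, beginning "QTcF = QT / [(heart\ rate/60)^{(1/3" and "QTcB = QT / [(heart\ rate/60)^{(1/2": QT is divided by the cube root, or the square root, of heart rate/60.

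Protocol 10.4 requires heart rate, QT and corrected QT to be recorded from each ECG, without saying which correction. SAP Appendix 2 contains a Grade 4 entry on corrected QT that includes "QTc ≥ 501 ms or >60 ms change from baseline".

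**The concern.** QT lengthens when the heart slows and shortens when it speeds up, which is why a corrected interval is computed at all. A category based on the raw change therefore mixes two things: a change in repolarization and a change in heart rate between two visits 26 weeks apart. It can flag a subject whose corrected interval has not moved, and it can miss one whose corrected interval has.

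The absolute QTcF and QTcB bands do not fill the gap. A subject who goes from 385 to 445 msec on QTcF has risen by 60 msec and enters none of them, because the lowest starts at 450. Only one post-baseline ECG is scheduled, so a misclassified subject is not corrected by a later reading. The heart-rate rows (below 50 and above 100 bpm) would not point to the cause either, since the changes that matter here lie between those limits.

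**Working it through.** The plan states no figure to reproduce, so the check takes constant or known QTcF values, computes the raw QT they imply, and applies the SAP's cut-offs.

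**Inputs.** Cut-offs of 30 and 60 msec: SAP 11.8.5. Heart rates of 60 to 90 bpm and QTcF of 380 to 440 msec: assumptions, as the documents contain no ECG data. Relation used: standard Fridericia, QTcF = QT/(60/HR)^(1/3), so QT = QTcF × (60/HR)^(1/3). For Bazett the exponent is 1/2. These are not the formulas as printed, which are taken up in step 4.

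**1. A flag created.** QTcF 405 at both visits, HR 80 then 60.
- QT at 80 bpm = 405 × (60/80)^(1/3) = 405 × 0.9086 = 368.0
- QT at 60 bpm = 405.0
- Raw change +37.0 msec, flagged; QTcF change 0

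Over QTcF 380 to 440 the same fall in heart rate gives +34.7 to +40.2 msec.

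**2. A change hidden.** QTcF 400 then 460, HR 70 then 85.
- QT at 70 bpm = 400 × (60/70)^(1/3) = 380.0
- QT at 85 bpm = 460 × (60/85)^(1/3) = 409.6
- Raw change +29.6 msec, in neither row; QTcF change +60

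**3. How large a heart-rate change is needed** (constant QTc 400, starting from 80 bpm).

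| Raw QT change | Fridericia | Bazett |
|---|---|---|
| +30 msec | fall to about 63 bpm | fall to about 68 bpm |
| +60 msec | fall to about 51 bpm | fall to about 58 bpm |

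A fall from 80 to 70 bpm gives only +16.5 msec (Fridericia) or +23.9 msec (Bazett), so small changes do not cross 30 msec by themselves.

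**4. The printed formula.** Dividing by (HR/60)^(1/3) applies the correction in the wrong direction. On the example in step 1:
- at 80 bpm: 368.0/(80/60)^(1/3) = 368.0/1.1006 = 334.3
- at 60 bpm: 405.0
- printed-QTcF change +70.7 msec, which falls in the 60 msec row

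On the example in step 2:
- at 70 bpm: 380.0/(70/60)^(1/3) = 380.0/1.0527 = 360.9
- at 85 bpm: 409.6/(85/60)^(1/3) = 409.6/1.1231 = 364.7
- printed-QTcF change +3.8 msec, where the true rise is 60

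In both directions the printed QTcF does worse than raw QT.

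**5. Frequencies under assumed variability.** Simulation of 400,000 pairs per setting; baseline HR normal (mean 75, SD 10 bpm), baseline QTcF normal (mean 410, SD 18 msec), SD of heart-rate change 7 to 10 bpm, SD of QTcF change 10 to 14 msec. All of these are assumptions.

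| Share flagged | Raw QT | Standard QTcF | QTcF as printed |
|---|---|---|---|
| No true change, 30 msec or more | 3.8%–10.3% | 0.1%–1.6% | 13%–21% |
| No true change, 60 msec or more | 0.1%–1.1% | – | 2%–7% |
| True rise 35 msec, mean HR rise 5 bpm, 30 msec or more | 34%–39% | 64%–69% | 25%–32% |

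Without the assumed 5 bpm mean rise, raw QT flags 55% to 56% in the last scenario. With no true change, at least 84% of the raw QT flags at 30 msec have a QTcF change below 30 msec.

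**The case against.** The strongest objection is to the obvious remedy. A reader might infer that replacing QT by QTcF in two rows is enough. It is not: the SAP defines QTcF by the printed formula, and step 4 shows that a change row on that definition is worse than the one it replaces. This stands in full, and the fix must deal with both.

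A reader might also infer that the secondary endpoint on the incidence of clinically significant ECG abnormalities is itself wrong in both directions. The documents do not support that. SAP 11.8.5 calls these rows potentially clinically significant; Protocol 10.4 and 11.5.2 leave clinical significance to the investigator, who records it as an adverse event. Nothing says the endpoint is computed from these two rows alone. The absolute QTc bands and a listing of flagged observations remain, and the general change-from-baseline summary can cover QTc descriptively.

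Nor is Appendix 2 good evidence that the SAP contradicts itself. Its Grade 4 entry also requires torsade de pointes, polymorphic ventricular tachycardia or signs of serious arrhythmia, so it is not a stand-alone 60 msec category. SAP 11.8.3.1 applies the grading only to listed hematology and chemistry parameters. The entry shows the 60 msec change attached to QTc, and no more.

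Finally, heart-rate noise falls on both randomized arms and no test or decision rule uses these rows. That limits the consequence. It does not make raw QT a sound measure of an individual's change.

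**Conclusion.** The point holds in limited form. Both categorical change rows are on uncorrected QT, no change category exists for QTcF or QTcB, and plausible heart-rate changes alone can create or hide a flag. This is easy to reach at 30 msec (a fall of about 17 bpm from 80 on Fridericia). At 60 msec it takes about 29 bpm from 80 on Fridericia, or 22 on Bazett.

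The direction follows from the correction relation and needs no data, to the extent that the relation holds in these subjects. The percentages depend on the assumed SDs and show only a plausible order of size. A claim that the rows mostly count heart-rate variation would need ECG data that the documents do not give.

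A descriptive safety table is affected. The primary immunogenicity analysis and the key secondary HbA1c analysis are not.

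**What to change.** In SAP 11.8.5, make these changes in one edit:

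- Define both change rows (30 to under 60 msec; 60 msec or more) on QTcF, and add the same rows for QTcB if Bazett is kept.
- Correct the printed formulas to QTcF = QT/[(60/heart rate)^(1/3)] and QTcB = QT/[(60/heart rate)^(1/2)]. Alternatively, use the corrected QT recorded under Protocol 10.4, after confirming which correction it carries.

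Do not move the rows to QTcF while leaving the formulas as printed.

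The cost is a few lines of SAP text, one table shell and the matching derivation. Heart rate, QT and corrected QT are already recorded, so no new data are needed.
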